|            | 
 
• Intervention-emergent AEs of special interest (eg, hypotension, anemia, hyperthyroidism).
 
• Change in vital signs (systolic and diastolic arterial blood pressure and pulse rate) and body weight from baseline to all assessed timepoints during the study.
 
• Intervention-emergent marked laboratory abnormalities.
 
• Change from baseline in forced vital capacity (FVC) and diffusing capacity of the lung for carbon monoxide (DLco).
 
• Change from baseline in supplemental oxygen rate.
 
• Change from baseline in arterial blood gas parameters.
 
 |

Refer to Section 8 for evaluations related to endpoints.

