5.1.1. Visit Windows

As participants do not always adhere to the protocol visit schedule, the following rules are applied to assign actual visits to analysis visits. Listed below are the visit windows and the target days for each visit. The period starts with the administration of the first dose of DB study treatment. The reference day is Study Day 1, which is the day of randomization. If a participant has 2 or more actual visits in one visit window, the visit closest to the target day will be used as the protocol visit for that visit window. The other additional visit(s) will not be used in the summaries or analyses,

but they can be used for determination of clinically important endpoints. If 2 actual visits are equidistant from the target day within a visit window, the later visit is used.

All assignments will be made in chronological order. Once a visit date is assigned to a visit window, it will no longer be used for a later time point except for the endpoint. Listed below (Table 4) are the visit windows and the target days for each visit defined in the protocol.

Table 4 Visit Windows for double-blind treatment period

Parameter	Scheduled Visit Number	Time Interval (label on output)	Time Interval (Day)*	Target Time Point (Day)
All parameters [§]	1	Screening	< 1	[-30 to -1]
	2	Baseline	<=1	1
RHC (including PVR) / DLco / Spirometry / Arterial blood gas	5	Week 26	2 to 280	183
All Other parameters	3	Week 12	2 to 112	85
	4	Week 20	113 to 161	141
	5	Week 26	162 to 228	183
	6	Week 39	229 to 364	274
	7	Week 65	365 to 546	456
	8	Week 91	547 to 728	638
	9	Week 117	729 to 910	820
	10	Week 143	911 to 1092	1002

§ RHC is collected only during the screening period, not at baseline. *Relative to Study Day 1; DLco = diffusing capacity for carbon monoxide; RHC = right heart catheterization.

It is likely that only few participants (or none) will have an assessment after visit 10 and therefore those data will not be used in summary statistics and will be listed only.

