5.6. Safety Analyses

All safety analyses will be based on the safety analysis set based on actual intervention received, unless otherwise specified. Analyses will be conducted for the entire study period only.

For all continuous safety variables, descriptive statistics by intervention group will include the N, mean, standard deviation, median, minimum, and maximum. Categorical variables will be summarized by intervention group using frequency counts and percentages.

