5.6.3.4. Other Safety Parameters

Descriptive statistics of values and changes from baseline in supplemental oxygen rate, DLCO, FVC and arterial blood gas will be summarized over time on the SAS by treatment group for the entire study period.

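### SAP Table 4 gives DLco and spirometry no analysis visit after Day 280, although SAP 5.6.3.4 calls for DLCO and FVC summaries over the entire study period

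*SAP*

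**What the plan says.** SAP 5.1.1 assigns actual visits to analysis visits through Table 4, headed "Visit Windows for double-blind treatment period". The row for "RHC (including PVR) / DLco / Spirometry / Arterial blood gas" has one post-baseline entry: Visit 5, Week 26, Day 2 to 280, target Day 183. All other parameters have eight adjoining windows, from Week 12 (starting Day 2) to Week 143 (ending Day 1092).

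Two further rules in 5.1.1 matter:

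- "If a participant has 2 or more actual visits in one visit window, the visit closest to the target day will be used", and "The other additional visit(s) will not be used in the summaries or analyses".
- The only rule that sends late data to listings concerns the far end of the schedule: "It is likely that only few participants (or none) will have an assessment after visit 10".

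For safety reporting, SAP 5.6 says "Analyses will be conducted for the entire study period only", and SAP 5.6.3.4 says "DLCO, FVC and arterial blood gas will be summarized over time on the SAS by treatment group for the entire study period".

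Protocol Section 3 lists change from baseline in FVC and DLco as a safety endpoint. The on-treatment schedule in Protocol 1.3.1 marks DLCO and spirometry at Screening, at Week 26 and in one further column after Week 39. Arterial blood gas has no such later mark, and the notes to Protocol Table 2 confine it to screening and Week 26.

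**The concern.** A single window suits RHC and blood gas, each of which has one scheduled post-baseline measurement on treatment. It does not suit DLco and spirometry, which are scheduled again later. A programmer who follows Table 4 would produce DLCO and FVC tables with one post-baseline point and no place for any value after Day 280. These are the lung-function values after the longest exposure, in a population with lung disease. SAP version 3.0 cut efficacy back to listings but kept these safety summaries, so the gap affects a table that the plan still intends to produce.

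**Working it through.** **Inputs.** Windows and target days come from SAP Table 4. Visit days come from Protocol 1.3.1. EOMOP timing (39 weeks ±1 month after the last participant's randomisation) and EOT timing (about 5 months after EOMOP) come from Protocol 4.1. One month is taken as 30 days; this is an assumption.

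**1. Reproducing the plan's windows.** For all other parameters the lower bounds are midpoints between neighbouring target days, rounded up where needed:

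- (85 + 141)/2 = 113
- (141 + 183)/2 = 162
- (183 + 274)/2 = 228.5, so 229
- (274 + 456)/2 = 365
- (456 + 638)/2 = 547
- (638 + 820)/2 = 729
- (820 + 1002)/2 = 911

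All seven match Table 4. The Day 280 bound does not follow this rule: the midpoint between Week 26 and Week 65 is (183 + 456)/2 = 319.5.

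**2. Days without a window.** Day 2 to 1092 contains 1092 − 2 + 1 = 1,091 days. For DLco and spirometry, Day 281 to 1092 is unassigned: 1092 − 281 + 1 = 812 days, and 812/1,091 = 74%. For all other parameters, 0 days are unassigned.

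**3. Where the later test falls.** The extracted schedule does not settle whether the late mark belongs to the six-monthly visit, EOMOP or EOT. Under the design as planned:

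| Reading of the late mark | Study day | Relation to Day 280 |
|---|---|---|
| Six-monthly visit | first at 456 ± 7, so 449 to 463 | always after |
| EOMOP | 274 + k (± 30) for a participant randomised k days before the last | nominal day after once k ≥ 7 (274 + 7 = 281); whole window after once k ≥ 37 (274 + 37 − 30 = 281) |
| EOT | about 274 + k + 150 = 424 + k; with EOMOP a month early, 394 + k | always after |

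Under each reading the late test is normally outside the window. The exception is the EOMOP reading for participants randomised close to the last one.

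**4. Whether the SAP intends listing only.** The only listing rule for late data starts after Visit 10 (Week 143), not after Day 280. SAP 5.6.3.4 does not restrict DLCO or FVC to Week 26. Section 5.1.1 allows a visit to be reused for an endpoint value, but no endpoint or last value is defined for these two tests. Actigraphy does have one (EOT, SAP Table 5).

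**The case against.** The strongest reply is that SAP 5.6.3.4 covers arterial blood gas in the same sentence. Blood gas has only one scheduled post-baseline measurement, so "over time" could mean baseline plus Week 26. The whole-study wording could likewise describe the reporting period, since SAP 1.2.1 merges the protocol's two analysis timepoints into one final analysis. This does not remove the conflict. Blood gas has no later scheduled test to lose; DLco and spirometry do, and nothing tells the programmer to leave it out.

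The second reply is about scale. The study stopped early, the report is synoptic, SAP 5.5.16 refers to a very limited number of participants, and late rows could be nearly empty. That stands, and it keeps the point modest.

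The third is that the schedule table is broken in extraction. That also stands. A reader might infer that the late mark is the six-monthly visit and that every such test falls at least 449 − 280 = 169 days past the window. Column offsets differ from row to row, so the documents do not support fixing the column; those figures hold only under that one reading.

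A reader might also infer that, for early stoppers, an off-drug Week 26 test pushes a premature-EOT test out of the table. That requires off-drug tests to be windowed at all. Table 4's heading refers to the treatment period and the SAP does not settle the matter, so the inference is not relied on here.

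**Conclusion.** The inconsistency is real and should be corrected. As written, Table 4 gives no analysis visit to DLco or spirometry after Day 280, while SAP 5.6 and 5.6.3.4 call for whole-study summaries and the protocol schedules a later test. The conclusion rests on the SAP text and on the late schedule mark, whichever of the three columns it belongs to.

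Its reach is limited to descriptive safety tables. It would be wrong to infer that data are lost altogether: the SAP keeps all listings, so the values should still appear there. No hypothesis test and no PVR result is affected. How many participants are affected cannot be worked out, because the documents give no randomisation dates and SAP 1.2 redefines EOMOP as a premature EOMOP, which for some participants may fall before Day 281.

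**What to change.** Split the Table 4 row.

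- **RHC and arterial blood gas:** leave unchanged.
- **DLco and spirometry:** keep Week 26 at Day 2 to 280, and add Week 65 (Day 281 to 546), Week 91 (Day 547 to 728), Week 117 (Day 729 to 910) and Week 143 (Day 911 to 1092). Keeping Day 280 means a delayed Week 26 visit carries the same label for lung function as for RHC and blood gas done at that visit. No Week 39 row is needed, as the schedule shows no DLco or spirometry test there.
- **One extra summary row:** change from baseline to the last on-treatment value. State the on-treatment cut-off and reconcile it with the rule of last dose plus 3 days in SAP 5.6.2 and with the 7-day window for the premature EOT visit. The row also captures a later on-treatment test within Day 2 to 280 that loses the Week 26 slot to a test closer to Day 183.

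If the sponsor wants Week 26 summaries only, SAP 5.6.3.4 must say so and state that later values are listed.

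The cost is one table edit and one summary row. Late rows will be sparse, and a test on Day 281 to 319 will be labelled Week 65 although it lies nearer Day 183 than Day 456 (midpoint 319.5).

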5.1.2. Study Day and Relative Day

Study Day 1 or Day 1 refers to the day of randomization. All efficacy and safety assessments at all visits will be assigned a day relative to this date.

Study day or relative day for a visit is defined as:

- Visit date - (date of Study Day 1) +1, if visit date is \geq date of Day 1
- Visit date - Date of Day 1, if visit date $<$ date of Day 1

There is no 'Day 0'

5.1.3. Baseline

Baseline is defined as the last observation on or before the day of first dose of study treatment.

5.1.4. Imputation Rules for Missing Date/Time of Onset/Resolution

Partial AE onset dates will be imputed as follows:

- If the onset date of an adverse event is missing day only, it will be set to:
 - First day of the month that the AE occurred, if month/year of the onset of AE is different than the month/year of the first dose of study treatment.
 - The day of first dose of study treatment, if the month/year of the onset of AE is the same as month/year of the first dose of study treatment and month/year of the AE resolution date is different
 - The day of first dose of study treatment or day of AE resolution date, whichever is earliest, if month/year of the onset of AE and month/year of the first dose of study treatment date and month/year of the AE resolution date are same
- If the onset date of an adverse event is missing both day and month, it will be set to the earliest of:
 - January 1 of the year of onset, as long as this date is on or after the first dose of study treatment
 - Month and day of the first dose of study treatment, if this date is the same year that the AE occurred
 - Last day of the year if the year of the AE onset is prior to the year of the first dose of study treatment,
 - The AE resolution date.
- Completely missing onset dates will not be imputed, but the event will be assumed to be treatment emergent unless otherwise indicated.

Partial AE resolution dates not marked as ongoing will be imputed as follows:

- If the resolution date of an adverse event is missing day only, it will be set to the earliest of the last day of the month of occurrence of resolution or the day of the date of death, if the death occurred in that month.
- If the resolution date of an adverse event is missing both day and month, it will be set to the earliest of December 31 of the year or the day and month of the date of death, if the death occurred in that year.
- Completely missing resolution dates will not be imputed.

Concomitant therapy start dates will be imputed as follows:

- If the start date is missing day only, it will be set to first day of the month.
- If the start date has the year, but is missing the month, it will be set to January 1.
- If the start date is completely missing, it will not be imputed

Concomitant therapy end dates will be imputed as follows:

- If the end date is missing day only, it will be set to last day of the month.
- If the year is supplied, but is missing the month, it will be set to December 31, or the date of death if this is earlier.
- If the end date is completely missing, it will not be imputed

For missing or partial assessment dates:

- For scheduled visits, the date will be set to the date closest to the scheduled date, within the range allowed by the partial dates. (For screening assessments, use day -8 as the scheduled date.)
- For unscheduled visits with partial dates:
 - if the day of first dose of study treatment is within the period, it will be set to the day after first dose;
 - otherwise, if the day of first dose of study treatment is within the period, it will be set to the day of first dose;
 - otherwise, if only the day is missing, it will be set to first of the month.

otherwise, if the year is supplied, but is missing the month, it will be set to January1.

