### OVERALL DESIGN

This is a prospective, randomized, double-blind (DB), placebo-controlled, multicenter, interventional study in men and women  $\geq 18$  and  $\leq 75$  years of age with SAPH. Study intervention will be up-titrated to allow

each participant to reach their individual maximum tolerated dose (iMTD), in the range of 200 µg to 1,600 µg twice daily. For participants with moderate hepatic impairment (Child-Pugh Class B) or who are concomitantly taking a moderate cytochrome P450 (CYP)2C8 inhibitor(s) the dosing frequency is once daily.

The study starts with the first Informed Consent Form (ICF) signed by the first participant and ends with the last safety follow-up telephone call (TC) or visit of the last participant. The study comprises the following periods:

- A screening period of up to 30 days: starts with the signature of the ICF and ends with the participant's randomization at Visit 2, Day 1. The screening period should last at least 14 days to allow collection of baseline data for daily life physical activity (DLPA), sleep parameters, and Pulmonary Arterial Hypertension-Symptoms and Impact (PAH-SYMPACT™).
- Intervention and observation periods:

A main observation period (MOP) that starts with the participants' randomization at Visit 2, Day 1 and with a titration phase of up to 12 weeks. Participants receive double-blind study intervention (selexipag or placebo) during this period. It ends on the day of the EOMOP visit. The EOMOP visit is the data cut-off for the primary efficacy and safety analyses. The EOMOP visit for all participants is planned at 39 Weeks ±1 month after randomization of the last participant. The duration of the MOP will be different for each individual participant and will depend on the time of each participant's individual date of randomization.

- Participants who prematurely discontinue study intervention before the EOMOP visit will continue to perform visits and assessments as scheduled until the EOMOP visit.
- For participants who prematurely discontinue study intervention before the EOMOP visit and who disagree to perform visits and assessments as scheduled until the EOMOP visit, long-term follow-up information regarding their survival status will be collected yearly until death or the time of EOMOP.
- Information on the required procedures to follow if participants discontinue the study intervention prematurely is provided in Section 7.1.

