1.2. Study Design

This is a prospective, randomized, double-blind (DB), placebo-controlled, multicenter, interventional study in men and women ≥ 18 and ≤ 75 years of age with SAPH. Study intervention will be up-titrated to allow each participant to reach their individual maximum tolerated dose (iMTD), in the range of 200 μg to 1,600 μg twice daily. For participants with moderate hepatic impairment (Child-Pugh Class B) or who are concomitantly taking a moderate cytochrome P450 (CYP)2C8 inhibitor(s) the dosing frequency is once daily.

[figure not shown]
The study starts with the first Informed Consent Form (ICF) signed by the first participant and ends with the last safety follow-up telephone call (TC) or visit of the last participant. The study comprises the following periods:

- A screening period of up to 30 days: starts with the signature of the ICF and ends with the participant's randomization at Visit 2, Day 1. The screening period should last at least 14 days to allow collection of baseline data for daily life physical activity (DLPA), sleep parameters, and Pulmonary Arterial Hypertension-Symptoms and Impact (PAH-SYMPACTTM).
- Intervention and observation periods:
 - A main observation period (MOP) that starts with the participants' randomization at Visit 2, Day 1 and with a titration phase of up to 12 weeks. Participants receive double-blind study intervention (selexipag or placebo) during this period. It ends on the day of the EOMOP visit. The EOMOP visit is the data cut-off for the primary efficacy and safety analyses. The EOMOP visit for all participants is planned at 39 Weeks ± 1 month after randomization of the last participant. The duration of the MOP will be different for each individual participant and will depend on the time of each participant's individual date of randomization.
 - Participants who prematurely discontinue study intervention before the EOMOP visit will continue to perform visits and assessments as scheduled until the EOMOP visit.
 - For participants who prematurely discontinue study intervention before the EOMOP visit and who disagree to perform visits and assessments as scheduled until the EOMOP visit, long-term follow-up information regarding their survival status will be collected yearly until death or the time of EOMOP.

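### A duplicated condition in SAP 5.1.4 can date an unscheduled result to the day after first dose when the record shows it was taken no later than first dose

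*SAP*

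**What the plan says.** SAP 5.1.4 has separate rules for scheduled and unscheduled assessments with missing or partial dates. For scheduled visits, "the date will be set to the date closest to the scheduled date, within the range allowed by the partial dates". The unscheduled rule has no such limit. It is a chain of branches:

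1. "if the day of first dose of study treatment is within the period, it will be set to the day after first dose"
2. "otherwise, if the day of first dose of study treatment is within the period, it will be set to the day of first dose"
3. "otherwise, if only the day is missing, it will be set to first of the month"
4. If the month is missing too but the year is known, 1 January of that year.

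What the imputed date decides is set in SAP 5.1.3: "Baseline is defined as the last observation on or before the day of first dose of study treatment". Under SAP 5.6.3.1, a post-baseline laboratory abnormality is treatment-emergent if it is worse than baseline, and always if baseline is missing. SAP 5.6.3.2 treats a missing baseline vital sign in the same way.

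**The concern.** Branches 1 and 2 share one condition, word for word, but assign different dates. A second branch that can never be used suggests that one of the conditions was mistyped. The one-day difference falls exactly on the cut between baseline and post-baseline: the day of first dose can be baseline, and the day after cannot.

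An abnormality that was present before or on the day of first dose could therefore be reported as having emerged on treatment. The same value would also be lost as a candidate baseline. This matters here because safety is what the SAP still summarizes, while efficacy is listed only (SAP 5.1). There is a plausible route for such a record: Protocol 10.2 allows an extra local blood sample before randomization to check eligibility, and SAP 5.6.3.1 uses local laboratory data to find marked abnormalities.

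**Working it through.** The plan gives no figure to reproduce, so the check is of the date logic.

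**Inputs.** The branches in SAP 5.1.4, read as an if/otherwise chain; the baseline definition in SAP 5.1.3; a period equal to the month (or year) that the record gives.

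**Rule as written, month recorded, every first-dose date in a 365-day year, record from the first-dose month:**
- Branch 2 is reached for 0 of 365 dates.
- The imputed date leaves the recorded month for 12 of 365 dates, the month-ends: 12 / 365 = 3.3%.

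**Rule with branch 1 testing the day after first dose:**
- Branch 2 is reached for those same 12 dates.
- The imputed date leaves the recorded month for 0 of 365 dates.
- The two versions differ for these 12 dates only.

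**Worked cases:**

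| First dose | Record | As written | Day after first dose tested |
|---|---|---|---|
| 15 March | March | 16 March | 16 March |
| 31 March | March | 1 April (not in March) | 31 March |
| 31 March | April | 1 April | 1 April |
| 31 December | that year only | 1 January of the next year | 31 December |

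In the second row the record allows 1 to 31 March, all on or before first dose, so the result belongs on the baseline side of the cut. The rule puts it on the other side. The fourth row is the same error with only the year recorded. In the third row the two versions agree by different branches, so the change does no harm there.

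**Scale.** If first-dose dates were spread evenly over the calendar and all 74 planned participants had been randomized, 74 × 12 / 365 = 2.4 would have a month-end first dose. An error also needs an unscheduled assessment in that same month with the day missing. The documents give no rate for that, and the study stopped before planned enrolment was complete.

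**The case against.** The best argument for leaving the rule alone is that it will probably never matter. Protocol Section 8 requires the dates of unscheduled visits and of sample collection to be recorded, and central laboratory results are transferred electronically. Laboratory samples are scheduled at Visits 1 and 2, so a missing baseline is unlikely, and with a baseline present a treatment-emergent flag needs a worse value. No hypothesis is tested, and SAP 5.5.16 itself notes how few participants there are. All of this stands and limits the size of the point. It does not make the imputed date right.

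Four stronger readings are tempting, but the documents do not support them:

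- **That the rule returns two answers.** The branches are joined by an otherwise, so it returns one date. The fault is that this date can be impossible.
- **That every partly dated unscheduled result is misplaced for a participant with a month-end first dose.** When only the day is missing, results from other months go to branch 3 or, as in the third row of the table, get the same date either way. They stay on the correct side of first dose.
- **That the Week 12 summary is distorted.** An imputed Day 2 falls in the Day 2 to 112 window, but SAP 5.1.1 takes the visit closest to Day 85, so any actual Visit 3 displaces it. Displaced visits may still be used for clinically important endpoints, so the treatment-emergent flag is the main exposure.
- **That the screening anchor is also wrong.** The SAP says "For screening assessments, use day -8 as the scheduled date", and also "The screening period should last at least 14 days to allow collection of baseline data", so Day -8 does not match the expected day of Visit 1. But that minimum is worded as a recommendation, and the protocol provides for "A screening period of up to 30 days". SAP Table 4 sets the screening target at Day -30 to -1, which contains Day -8. The anchor applies to screening assessments in general: with Visit 1 on Day -30 and actigraphy on Days -29 to -16, a screening catheterization could fall on Day -8. Moving the anchor to Day -14 would change no classification, since both days precede first dose.

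**Conclusion.** The rule is wrong as written: one branch is dead text, and in a definable case the other assigns a date that contradicts the record and moves a result across the baseline cut. The month-only case can arise for 3.3% of first-dose dates, and only for an unscheduled result from the first-dose month with the day missing. The year-only case needs a first dose on 31 December. The expected number affected is very small and may be zero. This is a minor correction to the safety reporting with no bearing on efficacy.

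The conclusion assumes that the branches are applied in order and that the period means the month or year recorded. That branch 1 was meant to test the day after first dose is an inference. It is supported by the fact that this reading gives branch 2 a purpose and removes every out-of-period date.

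**What to change.** In SAP 5.1.4, unscheduled visits with partial dates, change only the condition of the first branch, so that it asks whether the day after first dose falls within the period. Keep the date it assigns, and keep the second branch unchanged. Make the same change in the imputation program. No other imputed date moves, the screening anchor needs no change, and there is no downside.
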